### 3.8.2.4 Time to Next Therapy (TTNT)

The TTNT will be measured as the time from first treatment to the time of new systemic cGVHD treatment (which will be defined by clinical team review), censored by last response assessment or long term follow up assessment, whichever is the latest and available. TTNT will be analyzed by the Kaplan-Meier survival method as well as the landmark analysis at 6, 12, 18, and 24 months.

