17.4. Activity Analysis

The primary activity outcome will be the percentage of subjects who meet the OR criteria (PR + CR). This will be assessed overall (ie, any subject meeting the PR or CR criteria at any time point). For clarity, addition of new systemic therapy for cGVHD will be considered a KD025 treatment failure and will be considered progression of cGVHD for analysis purposes.

Secondary Endpoints

- Number and percentage of KD025 in subjects with steroid-dependent cGVHD who have a best response of PR or CR
- Change in cGVHD severity as based on the Physician-reported Global cGVHD Activity Assessment
- Change in symptom activity as based on cGVHD Activity Assessment Patient Self-Report
- Median FFS will be defined as the time from first dose of study drug to either the start of another treatment, relapse of the underlying disease, or death.
- Changes in corticosteroid and calcineurin inhibitor dose
- To evaluate DOR, which will be defined as the time of initial response until documented progression.
- To evaluate response by organ system. The response by organ system (PR and CR) will be assessed based on the 2014 NIH Consensus Development Project on Clinical Trials in cGVHD.
- Analyses of plasma PK of KD025 in subjects with cGVHD
- OS will be defined as the time from first dose of KD025 to the date of death due to any cause. Kaplan-Meier plots, descriptive statistics of OS and landmark OS at 6, 12, 18 and 24 months will be provided.
- TTNT will be defined as the defined as the time from the first dose of KD025 to the start of additional systemic cGVHD therapy Change in symptom burden/bother using the Lee cGVHD Symptom Scale.

Exploratory Endpoints

- Changes in the expression of several cytokines (including IL-17A, IL-21, and IL-2) in plasma after KD025 administration to subjects with cGVHD
- Changes in percentage of immune-cell subtypes (including Th17 and Treg cells) in whole blood after KD025 administration to subjects with cGVHD

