### **3.8.2.7 Failure-free Survival (FFS)**

Failure-free survival will be defined as the time from first dose of study drug to either the start of another new systemic treatment for cGVHD, relapse of the underlying

disease (both will be defined by clinical team review), or death. If no such events happen, FFS will be censored by last response assessment or long term follow up assessment, whichever is the latest and available. Failure-free survival will be analyzed by the Kaplan-Meier survival method as well as the landmark analyses at 6, 12, 18, and 24 months. In addition, analyses for the three components of FFS will also be provided.

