T	Descriptive Kaplan-Meier and landmark statistics for FFS (with cumulative failure rates for each of the 3 components FFS)	mITT
F	Kaplan-Meier plot for FFS (with cumulative failure rates for 3 components of failures)	mITT
L	Listing of failure events	mITT
Secondary Endpoint: Change in cGVHD severity as based on the Clinician-reported Global cGVHD Activity Assessment		
T	Maximal change from baseline in global severity rating based on Clinician-reported cGVHD Assessment	mITT
Secondary Endpoint: Symptom activity using the cGVHD Activity Assessment Patient Self-Report		
T	Maximal change from baseline in symptom activity (scored 0-10) based on cGVHD Activity Assessment Patient Self Report	mITT
T	Summary of severity rating on categorical status (none, mild, moderate, severe) based on cGVHD Activity Assessment Patient Self Report by visit	mITT
T	Descriptive statistics of cGVHD symptoms based on cGVHD Activity Assessment Patient Self Report (change of cGVHD symptom to a month ago) by visit	mITT
Secondary Endpoint: LSS score		

T/F/L	Title	Population
T	Descriptive statistics for LSS score	mITT Responder Non-responder
T	Summary of LSS Score (overall and each of seven domains) raw and change from baseline by visit	mITT Responder Non-responder
L	Listing of Lee Symptom Scale Score by subject, domain and visit	mITT
Subgroup analyses (subgroups are listed in section 3.8.4 Subgroup Analyses )		
T	Overall Response Rate by Subgroup	mITT
T	Descriptive Kaplan-Meier and landmark statistics for primary DOR by subgroup	mITT
F	Kaplan-Meier plot of all DOR by subgroup	mITT
L	Listing of PPI patients by cohort	mITT

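### TTNT is planned as Kaplan-Meier with deaths censored, so its landmark estimates will overstate the share of subjects starting next therapy if deaths come first

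*SAP*

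**What the plan says.** SAP section 3.8.2.4 gives TTNT one event: "The TTNT will be measured as the time from first treatment to the time of new systemic cGVHD treatment". Protocol section 17.4 has the same single event: "TTNT will be defined as the defined as the time from the first dose of KD025 to the start of additional systemic cGVHD therapy". In the SAP, a subject without that event is "censored by last response assessment or long term follow up assessment, whichever is the latest and available". The method is then: "TTNT will be analyzed by the Kaplan-Meier survival method as well as the landmark analysis at 6, 12, 18, and 24 months". Neither section mentions a subject who dies without new therapy, and no competing-risk method is named.

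Other endpoints in the SAP treat death differently:

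- **Tertiary duration of response (DOR).** It is also built on new systemic cGVHD therapy and, in Table 2, has in substance the same censoring rule as TTNT. Table 2 nevertheless lists death as an event.
- **Failure-free survival (FFS), section 3.8.2.7.** Its failures are new systemic therapy, relapse of the underlying "disease (both will be defined by clinical team review), or death". The section adds that "analyses for the three components of FFS will also be provided", and Table 5 lists the FFS output "with cumulative failure rates for each of the 3 components FFS". No estimator is named for these component rates.

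**The concern.** A subject who has died cannot start new therapy. Censoring that subject treats them as if they could still do so, at the same rate as those who remain under follow-up. The Kaplan-Meier complement then estimates the probability of next therapy in a population where nobody dies. A reader of a study report is likely to take a 12- or 24-month landmark as the share of treated subjects who went on to another therapy. For that reading the figure is too high (equivalently, the share reported free of next therapy is too low), and the gap widens with follow-up and with mortality.

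The SAP is also not consistent with itself. Two analyses with the same therapy endpoint and essentially the same censoring rule, TTNT and tertiary DOR, handle death in opposite ways without explanation.

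**Working it through.** **No figure to reproduce.** Neither document gives an expected next-therapy rate, a death rate or a landmark probability. Every rate below is an assumption. I take the landmark statistics to be Kaplan-Meier estimates at the stated times, since section 3.8.2.4 does not define them further.

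**Formulas**, for constant hazards h1 (new therapy) and h2 (death without new therapy) and time t in months:

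- 1-KM with death censored: 1 - exp(-h1·t)
- Cumulative incidence: h1/(h1 + h2) × (1 - exp(-(h1 + h2)·t))

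**Main illustration**, t = 24 and h1 = 0.03. 1-KM = 1 - exp(-0.72) = 51.3% in every row.

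| h2 per month | Cumulative incidence | Overstatement |
|---|---|---|
| 0 | 51.3% | 0 |
| 0.005 | (0.03/0.035) × (1 - exp(-0.84)) = 48.7% | 2.6 points |
| 0.010 | (0.03/0.040) × (1 - exp(-0.96)) = 46.3% | 5.0 points |
| 0.015 | (0.03/0.045) × (1 - exp(-1.08)) = 44.0% | 7.3 points |

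**Wider range.** Set each hazard from an assumed net 24-month probability p, h = -ln(1 - p)/24, with p of 30 to 60% for therapy and 5 to 30% for death. The 24-month overstatement runs from 0.7 points (30.0% against 29.3%) to 8.2 points (60.0% against 51.8%). At 6 months it is at most 0.9 points over the same range.

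**Counting example without a hazard model.** Take 16 subjects, with new therapy at months 3, 6, 9, 12, 15 and 20, deaths at months 5 and 11, and the other 8 followed beyond month 24.

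- KM at 24 months = (15/16)(13/14)(12/13)(10/11)(9/10)(8/9) = 0.584, so 1-KM = 41.6%.
- The share who started new therapy is 6/16 = 37.5%, which is also the cumulative incidence.
- If the two deaths are replaced by continued follow-up, both methods give 37.5%.

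**FFS components, conditional on the method.** Assume hazards of 0.03 (new therapy), 0.005 (relapse) and 0.005 (death) at 24 months.

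- 1-FFS = 1 - exp(-0.04 × 24) = 61.7%.
- If each component were done by 1-KM: 51.3 + 11.3 + 11.3 = 73.9%, more than the total failure rate on the same figure.
- If each is a cumulative incidence: 0.75 × 61.7 = 46.3% and 0.125 × 61.7 = 7.7% twice, which sum to 61.7%.

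**The case against.** Kaplan-Meier with death censored is a legitimate estimate of a net quantity under independent censoring, and it misleads only if presented as the actual proportion treated. This stands as a statement about the estimator. However, the SAP assigns no net interpretation to its landmarks, and the natural reading is the actual proportion.

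Death is not hidden from the analysis as a whole. It is an event in FFS and in all four DOR definitions in Table 2, and overall survival has the same four landmarks (SAP section 3.8.2.8). This is true and limits the harm, but none of those outputs corrects the TTNT estimate.

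The bias is small beside the sampling error. For a proportion near 50%, the 95% half-width is about 1.96 × √(0.25/16) = 24 points in a cohort of 16, and 1.96 × √(0.25/48) = 14 points overall, before any loss to censoring. This stands and keeps the point modest. The bias is nevertheless systematic, in a known direction, and avoidable.

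A reader might infer that the FFS component rates will also be wrong. The documents do not support that. The wording in Table 5 fits cumulative incidence at least as well as 1-KM, and death cannot be the censored event for the death component, where new therapy and relapse compete. A reader might also infer that comparisons between dose cohorts will be distorted. No cohort comparison of TTNT is specified, and the cohorts are enrolled sequentially, not randomized.

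**Conclusion.** The point holds for TTNT. The stated event and censoring rule together imply that death before new therapy is censored, although the SAP does not say so in words. The direction of the resulting bias is certain whenever such deaths occur. Its size cannot be known from the documents: it is about 3 to 7 points at 24 months under the main assumed hazards, small at 6 months, and zero if nobody dies first. It would be going too far to say that any reported TTNT probability is too high, because the documents contain none; this is a defect of the planned analysis.

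For the FFS components the finding is only that the estimator is unnamed. That calls for clarification and is not a demonstrated error.

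TTNT is a secondary, descriptive endpoint in an exploratory study. The change is worth making, but the primary conclusions do not depend on it.

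**What to change.** In SAP section 3.8.2.4, state that death before new systemic cGVHD therapy is a competing event. Estimate TTNT by cumulative incidence (Aalen-Johansen) with 95% confidence intervals at 6, 12, 18 and 24 months. Keep the Kaplan-Meier plot as supportive, labelled as censoring deaths.

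In section 3.8.2.7 and Table 5, state that the component failure rates are cumulative incidences of the first failure, with the other two components competing, so that they sum to 1-FFS. A footnote should explain that the new-therapy component can still differ from TTNT, because relapse competes in FFS but not in TTNT.

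The data are already planned. Long-term follow-up collects survival status and changes in cGVHD treatment about every 8 weeks (protocol section 8.8), and the sponsor undertakes to seek the date of death (protocol section 13.1.2). The cost is SAP wording, a standard software option and slightly more output.

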### **3.8.2.5 Corticosteroid Dose**

Corticosteroid doses on Day 1 of each treatment cycle will be presented as mg/kg/day prednisone equivalent dose. Descriptive statistics for the mITT Population, Responder and Non-responder Populations and subgroups defined by baseline corticosteroid dose level (upper and lower 50th percentiles) will be provided for:

- Systemic corticosteroid dose over time
- Change and percent change from baseline (Cycle 1 Day 1 [C1D1]) to the greatest corticosteroid dose reduction during KD025 treatment period
- Number and percentage of subjects who reduced systemic corticosteroid dose during KD025 treatment period
- Number and percentage of subjects who ever discontinued systemic corticosteroid usage during KD025 treatment period

If subjects are not using prednisone as the systemic corticosteroid, then the equivalent dose of 1 mg of prednisone will be determined according to following conversion ratios:

- 4 mg Hydrocortisone
- 0.8 mg Methylprednisolone
- 0.15 mg Dexamethasone
- 1 mg Prednisolone
- 0.8 mg Triamcinolone

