6.3. Overview of Study Design

This is a Phase 2a, dose-escalation, open-label study designed to evaluate the safety, tolerability, and activity of KD025 in subjects with steroid-dependent cGVHD and active disease in terms of PR and CR as defined by the 2014 NIH Consensus Development Project on clinical trials in cGVHD (see [Appendix B](#)). This study also is designed to use the Physician-reported global cGVHD Activity Assessment to evaluate cGVHD severity; use the cGVHD Activity Assessment Patient Self-Report to assess symptom activity (see [Appendix C](#)); evaluate FFS; evaluate OS; assess changes in corticosteroid and calcineurin inhibitor (CNI) dose; evaluate TTNT; and assess the PK of KD025 in subjects with cGVHD. Changes in symptom burden/bother will be documented using the Lee cGVHD Symptom Scale (see [Appendix D](#)). Changes in the expression of several cytokines (including IL-17A, IL-21, and IL-2) in plasma and percentages of immune-cell subtypes (including Th17 and Treg cells) in whole blood after KD025 administration to subjects with cGVHD.

Subjects who have signed an IRB/IEC-approved informed consent form, and met all of the inclusion/exclusion criteria ([Section 7.2](#) and [7.3](#)), will be enrolled. Approximately 48 subjects will receive orally administered KD025 200 mg QD (n = 16), KD025 200 mg BID (n = 16), or KD025 400 mg QD (n = 16). Study drug will be administered in 28-day cycles until disease progression or unacceptable toxicity occurs. For disease progression, subjects with a “Lack of Response (LOR) – Mixed” response assessment ([Appendix B](#)) may continue treatment with KD025 and remain on study if the investigator considers continued treatment to be in the subject’s best interest, only after approval from the medical monitor and documentation of the subject’s willingness to continue. Subjects may receive study drug treatment either in the inpatient or outpatient setting.

Prior to enrolling subsequent cohorts, the safety data in each previous cohort will be evaluated after 8 subjects have reached 2 months of treatment to assure there is no safety signal. As this is an open-label study, safety data will be continuously monitored. If $\geq 25\%$ of subjects in a cohort experience a [Common Terminology Criteria for Adverse Events \(CTCAE\)](#) v4.03 Grade 2 liver toxicity or a CTCAE v4.03 Grade 3 (or higher) AE in the same organ or body system, or if

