Response criteria will be assessed using the 2014 NIH Consensus Development Project for Clinical Trials in cGVHD criteria (CR, PR, or LOR [unchanged, mixed, or progression; see ([Lee et al., 2015](#))).

Activity in terms of cGVHD severity will be evaluated using the Physician-reported Global cGVHD Activity Assessment form (see [Appendix A](#)), while activity in terms of symptom burden will be evaluated using the cGVHD Activity Assessment - Patient Self Report (see [Appendix C](#)). Failure-free survival, OS and TTNT will be evaluated at the same time points. Changes in corticosteroid and CNI dose will be documented as they occur on the appropriate eCRF. Changes in symptom burden/bother will be documented using the Lee cGVHD Symptom Scale (see [Appendix D](#)).

See [Section 10](#) for additional information on response assessment.

Prior and Concomitant Medications

All concomitant medications, including systemic steroids and CNIs, are to be collected from time the subject signs the ICF throughout the subject's participation in the study. See [Section 15](#) for additional information.

Adverse Event Assessments

Information regarding the occurrence of AEs will be collected from the time the subject signs the ICF throughout their participation in the study, including a period of 28 days after last dose of

study drug. AE severity will be determined using the CTCAE v4.03 grading scale. Also, see [Appendix G](#) for criteria for determining relationship of AE to study drug.

Note: Adverse events resulting in a subject’s permanent discontinuation from the study, regardless of seriousness or relationship to study drug, **MUST** be promptly reported to the sponsor.

See [Section 13.2](#) for stopping rules for this study.

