10.6. Corticosteroid and Calcineurin Inhibitor Use

Corticosteroid and CNI dose will be collected throughout the study and changes in requirements will be documented. Corticosteroids may be tapered at the discretion of the investigator after 4 weeks of KD025 administration. In addition, data on use of non-immunosuppressive therapy, such as ECP, will be collected as well.

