**SIGNATURE PAGE**

**DOCUMENT HISTORY**

Version	Author	Description
1.0		Nov 30, 2017 New Document
2.0		Revision The primary reasons for this new version include: 
 
• Change of study design: expansion cohort removed. In its place, there will be another new randomized, open-label Phase 2 study, KD025-213: “A Phase 2, Randomized, Multicenter Study to Evaluate the Efficacy and Safety of KD025 in Subjects with Chronic Graft Versus Host Disease After At Least 2 Prior Lines of Systemic Therapy”
 
• Add more definitions of duration of response in accordance with FDA type B meeting held on 01 May 2019
 
• Rearrange and add some secondary efficacy endpoints
 
• Correct the calculation of symptom score for the Lee cGVHD Symptom Scale
 

2.1		Revision The primary reasons for this new version include: 
 
• Add subsection of “Missing event dates”
 
• Change/clarify censoring rule for duration of response (DOR), time to new therapy (TTNT) and failure free survival (FFS)
 
• Clarify the definition of discontinuation of Corticosteroid
 

2.2		Revision The primary reasons for this new version include: 
 
• Add overall survival analysis as a secondary efficacy endpoint
 
• Add refractory to prior line status into subgroup analysis
 

2.3		Revision The primary reason for this new version is to move Lee symptom scale score from exploratory to secondary endpoint.

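### Corticosteroid dose is summarised from one day per 28-day cycle, and the greatest reduction has neither a minimum duration nor a stated data source

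*SAP*

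**What the plan says.** Change in corticosteroid dose is a secondary endpoint. SAP 3.8.2.5 opens with the only dose variable that it defines: "Corticosteroid doses on Day 1 of each treatment cycle will be presented as mg/kg/day prednisone equivalent dose". It defines no average, cumulative or daily dose. Besides dose over time, it lists three statistics:

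- The best value reached, worded as "Change and percent change from baseline (Cycle 1 Day 1 [C1D1]) to the greatest corticosteroid dose reduction during KD025 treatment period".
- A count, with percentage, of those whose systemic steroid dose came down at some point on KD025.
- A matching count of those who ever stopped systemic steroid while on KD025.

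All three refer to the whole treatment period. None names its data source, and none sets a minimum time for which a reduction or a stop must last. The SAP document history for version 2.1 includes the entry "Clarify the definition of discontinuation of Corticosteroid", but 3.8.2.5 contains no rule on time off steroid. In SAP Table 5 the dose summary with change from baseline is by visit, and the dose listing is by subject and visit.

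The protocol collects more than this uses. Section 9.1 says "Changes in corticosteroid and CNI dose will be documented as they occur on the appropriate eCRF", and Section 10.6 says "Corticosteroid and CNI dose will be collected throughout the study and changes in requirements will be documented". Section 10.6 also leaves tapering after the first 4 weeks to the investigator, so doses can change at any point in a cycle.

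**The concern.** There are two separate weaknesses, with different causes.

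The first comes from sampling. A summary built on Day 1 readings cannot show a steroid course that starts and ends between two Day 1 visits. Dose over time is the one steroid statistic in which an increase could appear, since the other three register only decreases. Extra steroid between visits can therefore leave no trace in the endpoint tables.

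The second comes from the definition. The greatest reduction is an extreme value with no duration rule, so a low dose held for a day counts as much as one held for months. The count of subjects who ever stopped steroid is open in the same way.

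The unstated source adds a practical problem: two programmers could follow 3.8.2.5 and produce different results. Steroid sparing is likely to be read as evidence of activity, and the trial has no control arm against which an inflated best value could be judged.

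**Working it through.** The documents give no power, precision or expected value for the steroid endpoint, so there is no planned figure to reproduce.

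**Inputs from the documents.** Dose is read on Day 1 of each cycle (SAP 3.8.2.5). The cycle length comes from Protocol 6.3: "Study drug will be administered in 28-day cycles until disease progression or unacceptable toxicity occurs".

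**Inputs that are assumptions.** Course lengths of 5, 7 and 14 days, starting on a random day of the cycle; doses of 1.0 and 0.2 mg/kg/day; and 2%, 5% or 10% of days with a low or zero dose, independent across days. The documents give none of these. Readings are taken as exactly 28 days apart, ignoring the 3-day visit window.

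**Step 1. Share of days read.** 1/28 = 3.6%.

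**Step 2. Courses missed by the Day 1 summary.** A course of L days includes a Day 1 with probability L/28, so it is missed with probability 1 − L/28.

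- L = 5: 1 − 5/28 = 82%
- L = 7: 1 − 7/28 = 75%
- L = 14: 1 − 14/28 = 50%
- L = 28 or more: 0%

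**Step 3. What a missed course does to one subject's record.** Take 14 days at 1.0 on a background of 0.2 mg/kg/day. The cycle mean is (14 × 1.0 + 14 × 0.2)/28 = 0.6, while the Day 1 readings on either side can both be 0.2.

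**Step 4. Noise or bias?** With random timing the expected Day 1 reading is 0.5 × 1.0 + 0.5 × 0.2 = 0.6, equal to the cycle mean. The Day 1 average is then imprecise but not biased.

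**Step 5. The extreme value.** If a share q of days is low, the chance that at least one of k readings falls on a low day is 1 − (1 − q)^k.

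| Share of low days | 6 Day 1 readings | 12 Day 1 readings |
|---|---|---|
| 2% | 11% | 22% |
| 5% | 26% | 46% |
| 10% | 47% | 72% |

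If the full daily record is used instead, 12 cycles give 12 × 28 = 336 readings. At q = 5% the chance is then nearly 100%. The weakness is present under either source, and more likely under the fuller one. Switching to daily data alone would not cure it.

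**Step 6. Effect of averaging.** For a subject otherwise on a steady dose d, one day at zero gives a cycle mean of (27/28)d, a reduction of 1/28 = 3.6%. Scored as a single reading, the same day is a 100% reduction.

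**The case against.** The strongest reply is that the SAP ties only the presentation of dose to Day 1. The reduction and discontinuation bullets cover the treatment period and may well be meant to use the full record. SAP Table 4 also plans a table and a by-subject listing of concomitant corticosteroids for cGVHD, where courses between visits could be seen. A by-visit dose display is ordinary practice, and this is one descriptive secondary endpoint in an uncontrolled Phase 2a trial, with no test attached to it.

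Most of that stands, and it limits the point. Three stronger readings are tempting, and the documents support none of them:

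- *That every steroid statistic rests solely on Day 1 readings.* For the three reduction and discontinuation bullets the text is ambiguous. The fault there is the missing statement of source.
- *That missed courses and the extreme value both work in KD025's favour.* Step 4 shows that random timing makes the Day 1 mean noisy rather than biased. Day 1 readings can also miss temporary reductions. The single-day baseline can err either way: a course that ended just before C1D1 goes unseen, which lowers baseline relative to recent use and understates the reduction. A one-way effect can be claimed only for a brief low dose entering the greatest reduction.
- *That alternate-day dosing would often be scored as a complete stop.* The documents describe no such regimen. Dose is expressed as a daily rate, and nothing says that an off day would be entered as zero.

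The reply leaves two things unanswered. The Table 4 outputs report medication use and are not an analysis of the dose endpoint. And no reading of 3.8.2.5 supplies a minimum duration.

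**Conclusion.** The concern holds in a limited form. The SAP summarises steroid dose from 3.6% of treatment days although changes are recorded as they occur. It measures the greatest reduction from one baseline day with no duration rule, and does not say which data feed the reduction and discontinuation statistics.

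The structural points follow from the text and need no assumption. The sizes do. The miss rates of 75% and 50% rest on assumed course lengths and random timing, and the 11% to 72% range in Step 5 rests on assumed shares of low days. How often either happened in this trial cannot be told from the documents.

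The correction is worth making before the steroid tables are interpreted, but it does not touch the primary endpoint.

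**What to change.** Amend SAP 3.8.2.5 and the corticosteroid rows of Table 5 as follows.

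1. Compute the mean daily prednisone-equivalent dose for each cycle from the recorded start, stop and change dates. Use it for dose over time and for the greatest reduction. Average a final partial cycle over its available days and flag it.
2. Take baseline as the mean over the available recorded pre-dose days, up to 14, and flag shorter windows. A full 14 days is not guaranteed, because medication collection starts at consent and screening has no minimum length.
3. State the data source for the counts of subjects who reduced and who ever discontinued. Beside each, report how many kept the reduction, or stayed off steroid, for at least one full cycle.
4. Keep the Day 1 doses as a by-visit display.

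The cost is SAP wording and extra derivation from the dose record, with no new data collection. The best-reduction figures will probably be slightly less favourable, because a brief low dose will no longer set them.
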